### **2.3 Primary Endpoints**

The primary endpoint will be evaluation of toxicity, adverse events and reportable serious adverse events, i.e. grade 3 or higher, as defined by the NCI Common Toxicity Criteria for Adverse Events (CTCAE v. 5.0). RTOG/EORTC Radiation Toxicity Grading is standard of care at Beaumont Hospital for all radiation patients and CTCAE is the standard for reporting & publications. These criteria comprise of various parameters, including performance status, motor function, sensory function, general mental status, nausea/vomiting, hearing loss, xerostomia, and skin toxicity [51]. The CTCAE are cancer-specific and will be supplemented by information from neurocognitive testing using MMSE and ADAS-Cog. The tests will be administered by an appointed, trained site professional at baseline and at 6 weeks, 3 months, 6 months, and 12 months during follow-up. In the context of radiation oncology, the optimal time period for assessing cognitive impairment is within >6 months to 1 year [52,53].

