## **3.0 Methodology**

### ***3.1 Dose Levels and Sample Size Calculation***

In the context of this pilot study, traditional levels of  $\alpha$  (the Type I error rate) and  $\beta$  (the Type II error rate) are inappropriate since the objective of the research is not to provide definitive support for one treatment over another. In trials of safety such as this the objective is to show that the tested intervention produces a safety profile equal to a known standard therapy.

The nearest well-documented clinical situation to this novel study is the use of prophylactic cranial irradiation (PCI) in patients with limited disease small cell lung cancer (SCLC). Between September 1999 and December, 2005, 720 patients with limited-stage SCLC in complete remission after chemotherapy and thoracic radiotherapy from 157 centers in 22 countries were randomly assigned to a standard (n=360, 25 Gy in 10 daily fractions of 2.5 Gy) or higher PCI total dose (n=360, 36 Gy) delivered using either conventional (18 daily fractions of 2 Gy) or accelerated hyperfractionated (24 fractions in 16 days with two daily sessions of

1.5 Gy separated by a minimum interval of 6 hours) radiotherapy [54,55]. In this study 52% of patients experienced acute toxicity during PCI: headache in 85 patients in the 25 Gy group (24%) and 99 patients in the 36 Gy group (28%), respectively, fatigue in 106 (30%) and 121 (34%)

**Fig. 2** Upper limit of the  $100 \times (1 - \alpha)\%$  one-sided confidence interval for the true underlying adverse event rate,  $\pi$ , for increasing sample sizes when zero events of interests are observed

patients, insomnia in 14 (4%) and 13 (4%) patients, and nausea or vomiting in 80 (23%) and 101 patients (28%), with no significant differences between the two groups. Only two patients in the higher-dose group interrupted PCI because of acute toxicity: one because of grade 2 nausea or vomiting, and one because of scalp dermatitis. There were five serious adverse events, all of which occurred in the 25 Gy

group: one death (2 months after PCI) with undocumented neurological deterioration, one generalized seizure (12 months after PCI) treated with no sequelae, one transient ischemic attack (6 months after PCI), one bilateral cataract (29 months after PCI), and one death due to generalized seizure in a patient treated for epilepsy (29 days after PCI).

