### **3.9. Radiation On-Treatment Monitoring and Adverse Events**

Radiotherapy will be continued without interruption if at all possible as prescribed. If the sum of total radiotherapy interruptions exceeds seven normally scheduled treatment days, the treatment will be considered an unacceptable deviation from the protocol. This patient should

be reported to the principal investigator, and the patient will not be considered for final data analysis. Patients who do not complete a complete, total course of study radiotherapy will be replaced in the study in order to have 15 evaluable patients in each arm.

Patients will be monitored weekly by the treating radiation oncologist for the duration of radiotherapy and at regular intervals following radiotherapy. Scheduled post treatment visits are at 6 weeks, 3, 6 and 12 months. At each visit, the patient will undergo an interval history and physical exam and completion of Common Terminology Toxicity Criteria (Version 5.0), and RTOG toxicity scoring to assess any toxicity associated with this study. The RTOG toxicity scoring is done as radiation/oncology standard of care at Beaumont. This will include not only the effects on the CNS but any general adverse effects which may or may not be related to the treatment delivered. Each patient will be assigned a baseline score for skin, eye, ear and CNS and this will be monitored and evaluated during and after treatment for both acute and late toxicity. All adverse events will be recorded on an Adverse Event Reporting Form. The known risks associated with whole brain irradiation at the dose levels described may include, but are not limited to 1) hair loss, 2) decreased hearing, 3) nausea, 4) vomiting and 5) visual changes and 6) skin reactions. The grade or severity of adverse event that is common with the planned radiation dose for this trial based on the RTOG Common Toxicity Criteria are skin (Grade 1), CNS (Grade 1), ocular (Grade 0) and brain (Grade 1). All related/possibly related Grade >3 Toxicities will be reported as unexpected in severity to the IRB and monthly to the DSMB.

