**Hearing Loss**

- Grade 0, None
- Grade 1, Subjective change in hearing in the absence of documented hearing loss
- Grade 2, Hearing loss but hearing aid or intervention not indicated; limiting instrumental ADL.
- Grade 3, Hearing loss with hearing aid or intervention indicated
- Grade 4, Decrease in hearing to profound bilateral loss; non-servicable hearing.

Additional hearing loss since treatment  No  Yes

Other ear toxicity not listed above \_\_\_\_\_

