**CNS Toxicity:**

**Fatigue**

- Grade 0, None
- Grade 1, Fatigue relieved by rest
- Grade 2, Fatigue not relieved by rest; limiting instrumental ADL
- Grade 3, Fatigue not relieved by rest, limiting self care ADL

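### The primary endpoint defines a serious adverse event by CTCAE grade, which merges severity with seriousness, and Section 3.9 reports at a different grade cut

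*Combined protocol and SAP*

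**What the plan says.** Section 2.3 (Primary Endpoints) has a broad scope: "The primary endpoint will be evaluation of toxicity, adverse events and reportable serious adverse events". It then defines the last category by grade alone: "reportable serious adverse events, i.e. grade 3 or higher, as defined by the NCI Common Toxicity Criteria for Adverse Events". The supplied text gives no other criterion for seriousness.

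Section 3.9 covers recording and reporting. On recording: "All adverse events will be recorded on an Adverse Event Reporting Form". On reporting: "All related/possibly related Grade >3 Toxicities will be reported as unexpected in severity to the IRB and monthly to the DSMB".

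The Appendix III worksheet grades each toxicity by symptoms, limits on daily living and need for intervention. Two of its rows read "Grade 3, Hearing loss with hearing aid or intervention indicated" and "Grade 3, Fatigue not relieved by rest, limiting self care ADL".

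Section 3.1 names prophylactic cranial irradiation (PCI) as the nearest documented situation, states the aim of a safety profile on a par with a standard therapy, and lists five serious events from a trial of 720 patients. One of them is "one generalized seizure (12 months after PCI) treated with no sequelae". No grades are given for the five, and no definition of serious as that trial used it.

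**The concern.** Severity and seriousness are different attributes. The first is a position on a graded scale. The second, as trials normally use it, is a classification by outcome: death, threat to life, hospital admission, lasting disability, or another medically important consequence. An event can have either without the other. By writing one as the meaning of the other, Section 2.3 labels some Grade 3 findings serious that need not be, and withholds the label from serious events of lower grade.

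This is the primary endpoint of a safety study whose analysis is descriptive, so the event tables are the main result. If the table headed serious adverse events is really a table of Grade 3 or higher events, readers will take it for something else, and nothing in it will show which lower-grade events had serious consequences.

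The reporting text adds a second difficulty. Section 2.3 calls Grade 3 reportable, while Section 3.9, read literally, reports only grades above 3 and only when related or possibly related.

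**Working it through.** **1. What the label counts.** Divide patients in a cohort into four cells by whether they had a serious event (outcome criteria) and whether they had an event of Grade 3 or higher. For simplicity take one event per patient.

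| | Grade 3 or higher | Grade 1-2 |
|---|---|---|
| Serious by outcome | a | b |
| Not serious by outcome | c | d |

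- Serious tally under Section 2.3: a + c. This is simply the Grade 3 or higher count under another name.
- Serious tally by outcome: a + b.
- Difference: (a + c) - (a + b) = c - b.

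The difference can have either sign. It can also be zero when b and c are both above zero, so equal totals would not show that the same patients were counted. The documents give no values for b or c.

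**2. Both off-diagonal cells can occur.** Cell c: the hearing-aid and fatigue rows of Appendix III reach Grade 3 without requiring admission, threat to life or lasting disability. Cell b: the worksheet names hospitalization only in the Grade 3 rows for nausea and vomiting. An admission for any other reason does not by itself raise the grade there.

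**3. Where lower-grade serious events go.** Section 2.3 includes all toxicity and adverse events, and Section 3.9 records all of them. Cell b is therefore captured, but not tallied as serious.

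**4. The two grade cuts.**

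| | Section 2.3 | Section 3.9 |
|---|---|---|
| Grade 3 | included | excluded as written |
| Grade 4 and above | included | included |
| Relatedness required | no | yes, at least possibly related |

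**5. The plan's own figures.** Section 3.1 gives one-sided upper limits for 0 events in 15 patients. With the exact limit 1 - alpha^(1/15):

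- 99%: 1 - 0.01^(1/15) = 26.4%
- 95%: 1 - 0.05^(1/15) = 18.1%
- 90%: 1 - 0.10^(1/15) = 14.2%

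All three agree with the plan. They depend only on n = 15 and zero events, so redefining serious changes none of them. The stopping rules in Section 3.12 use attributed death, grade, amyloid PET and cognitive scores; none uses the label serious.

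**6. The PCI events.** Section 3.1 gives five events, all in the 25 Gy group: 5/720 = 0.69% overall, or 5/360 = 1.39% of that group. Two were deaths. Taking a death as above Grade 3, and the other three as unknown because no grades are given, between 2 and 5 of the five would meet the Section 2.3 definition: 2/720 = 0.28% to 0.69%, or 2/360 = 0.56% to 1.39%. Non-serious Grade 3 events in that trial are not reported in Section 3.1, so its full Grade 3 or higher rate cannot be computed. The cataract occurred at 29 months, against 12 months of follow-up here; without it the figures are 4/720 = 0.56% or 4/360 = 1.11%.

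**The case against.** The strongest reply is that little is lost. Every adverse event is inside the primary endpoint and goes on a form. Sections 3.9 and 5.0 also send a rise of 2 or more points to the DSMB within a week, so if those points are toxicity grades, a Grade 2 event from a baseline of 0 would be reviewed. A reader might infer that medically important lower-grade events are missed. The documents do not support that; only their classification as serious is affected.

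A reader might also infer that the count cannot be compared with the PCI events. That too goes beyond the text. Section 3.1 is silent on how that trial defined serious, so the definitions may differ or may agree. Nor does the plan specify a comparison: Section 3.1 moves to zero-event limits and calls the assessment descriptive. Fifteen patients could not show equality under any definition, since the 18.1% limit is about 13 times 1.39% and 26 times 0.69%.

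It is tempting to size the problem by moving one event into the tally, which raises the 95% upper limit from 18.1% (0 of 15) to 27.9% (1 of 15). The arithmetic is right, but the documents do not say how many events would move, and step 1 shows that movement can go either way.

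Three further cautions stand. The end of Section 5.0 is not in the supplied text and the adverse event form is not shown, so it cannot be said that the plan nowhere records seriousness. The worksheet's Grade 3 and Grade 4 rows already overlap with outcome criteria in places, and a hearing loss could in a given patient be judged a lasting disability. Finally, the sign in Section 3.9 may be a slip for at or above, and that section may describe a narrower reporting channel than Section 2.3. None of this removes the definition written in Section 2.3; a seriousness criterion elsewhere would conflict with it.

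**Conclusion.** The point holds as a misdefinition within the primary endpoint. Followed as written, Section 2.3 yields a serious-event tally that is the Grade 3 or higher count relabelled: it can include non-serious Grade 3 findings and leaves lower-grade serious events unclassed. The grade cuts in Sections 2.3 and 3.9 disagree on whether Grade 3 is reportable and must be reconciled. Comparability with the five PCI events is not established, because their definition and grades are not given and one arose well after the 12-month window.

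The effect is on labelling, reporting and interpretation. Its numerical size is unknown. The conclusion rests on the usual outcome-based meaning of serious and on the supplied text of Sections 2.3 and 3.9 and Appendix III.

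**What to change.** In Section 2.3, remove Grade 3 or higher as the definition of serious and define seriousness by outcome criteria, whatever the grade. Record seriousness and CTCAE v5.0 grade as separate variables. If the form or the rest of Section 5.0 already does this, refer to it.

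Report two counts per cohort: patients with any Grade 3 or higher event, and patients with any serious adverse event of any grade.

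Reconcile the reporting cut in Section 3.9 with Section 2.3, including whether relatedness is required; which cut applies is for the sponsor to decide.

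Make no formal comparison with the PCI count. If the two are shown side by side, state that the PCI definition is unknown and that follow-up differs.

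The cost is a wording change in Sections 2.3 and 3.9, one data field if it is not already collected, and one more line in the safety table. The small downside is that some lower-grade events will be added to the serious-event report.

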### **2.4 Secondary Endpoints**

- 1) Neurocognitive testing will be used to assess changes in cognitive function using the MMSE and ADAS-Cog. The tests will be administered by an appointed, trained site professional at baseline and at 6 weeks, 3 months, 6 months, and 12 months during follow-up.
- 2) Quality of life will be monitored via questionnaires completed by the patient prior to the start of irradiation and at 6 weeks, 3 months, 6 months, and 12 months during follow-up. Specific questionnaires include the QOL-AD and QUALID, which have been established as sensitive measures of various parameters of quality of life.
- 3) A pretreatment and post treatment (4 months) Amyvid PET/CT scan will be carried out to determine if there are any correlations between neurocognitive /QOL test results and amyloid number, size and location and changes after treatment.

[figure not shown]
## **3.0 Methodology**

### ***3.1 Dose Levels and Sample Size Calculation***

In the context of this pilot study, traditional levels of  $\alpha$  (the Type I error rate) and  $\beta$  (the Type II error rate) are inappropriate since the objective of the research is not to provide definitive support for one treatment over another. In trials of safety such as this the objective is to show that the tested intervention produces a safety profile equal to a known standard therapy.

The nearest well-documented clinical situation to this novel study is the use of prophylactic cranial irradiation (PCI) in patients with limited disease small cell lung cancer (SCLC). Between September 1999 and December, 2005, 720 patients with limited-stage SCLC in complete remission after chemotherapy and thoracic radiotherapy from 157 centers in 22 countries were randomly assigned to a standard (n=360, 25 Gy in 10 daily fractions of 2.5 Gy) or higher PCI total dose (n=360, 36 Gy) delivered using either conventional (18 daily fractions of 2 Gy) or accelerated hyperfractionated (24 fractions in 16 days with two daily sessions of

1.5 Gy separated by a minimum interval of 6 hours) radiotherapy [54,55]. In this study 52% of patients experienced acute toxicity during PCI: headache in 85 patients in the 25 Gy group (24%) and 99 patients in the 36 Gy group (28%), respectively, fatigue in 106 (30%) and 121 (34%)

**Fig. 2** Upper limit of the  $100 \times (1 - \alpha)\%$  one-sided confidence interval for the true underlying adverse event rate,  $\pi$ , for increasing sample sizes when zero events of interests are observed

patients, insomnia in 14 (4%) and 13 (4%) patients, and nausea or vomiting in 80 (23%) and 101 patients (28%), with no significant differences between the two groups. Only two patients in the higher-dose group interrupted PCI because of acute toxicity: one because of grade 2 nausea or vomiting, and one because of scalp dermatitis. There were five serious adverse events, all of which occurred in the 25 Gy

group: one death (2 months after PCI) with undocumented neurological deterioration, one generalized seizure (12 months after PCI) treated with no sequelae, one transient ischemic attack (6 months after PCI), one bilateral cataract (29 months after PCI), and one death due to generalized seizure in a patient treated for epilepsy (29 days after PCI).

However, at the doses of radiation initially being used in this study (10 Gy) we are unlikely to evoke the common toxicity criteria seen at higher doses. Therefore, we have used the approach of Carter and Woolson [56] whose simple expression has utility for the generation of confidence intervals when zero events are observed. Fig. 2 illustrates, for relatively small sample sizes, there is a large amount of uncertainty. It is critical to convey this uncertainty in the findings and to guard against inferring a potential treatment is harmless when no adverse effects of interest are observed with limited data. Based on this relationship we have chosen an initial cohort of 15 patients to be enrolled in the first treatment scheme (2 Gy x 5 fractions). The first cohort of patients will be followed for 12 months after completion of treatment to assess safety and any toxicity/adverse events associated with treatment. Using this approach, [name] (biostatistician) has calculated the upper confidence limits for the event rate when there are 0 events in a group of fifteen distinct patients. The method is consistent with what appears in the classical statistical literature for one-sided confidence limits. Supposing that no events are observed in the results from 15 distinct patients, then the following statements can be made:

- With 99% confidence, the true underlying adverse event rate  $\pi$  does not exceed 26.4%.
- With 95% confidence, the true underlying adverse event rate  $\pi$  does not exceed 18.1%.
- With 90% confidence, the true underlying adverse event rate  $\pi$  does not exceed 14.2%.

The second treatment arm will not be used until the last patient in the first dose arm has completed all follow up. At that point a second cohort of 15 patients will be enrolled in the second dose arm (2 Gy x 10 fractions). The second cohort will undergo a similar stand-alone post-treatment assessment. The starting dose group was chosen as the regimen most commonly used in our pre-clinical studies of AD whilst, the 2 Gy x 10 fractions was chosen as it represents the most commonly used protocol to treat systemic amyloidosis and was the most effective schedule in our preclinical studies of plaque reduction (Table 1) .

As this is a pilot study comprising of two groups of 15 patients, the statistical assessment of endpoints will be descriptive and not inferential. This is a pilot study which is a requisite initial step in exploring an innovative application of radiation treatment and as such its goal is to inform feasibility and identify modifications needed in the design of a larger ensuing hypothesis testing study. In this study we are not testing hypotheses due to the limited state of knowledge about radiation treatment in this population of patients and the FDA-mandated sample size.

### **3.2 Study Design**

This pilot study is a prospective, dose-escalating phase I study that will investigate the safety of low dose external beam radiation of patients with probable moderate stage Alzheimer's Disease. Patients who meet all eligibility requirements and consent to participate in this trial will receive either 10 or 20 Gy delivered in daily 2 Gy fractions using standard whole brain radiotherapy.

### **3.3 Patient Selection**

#### **3.3.1 Recruitment to the study**

Patients will be referred from clinicians in the S.E. Michigan area to 2 institutions, Beaumont-Royal Oak and Beaumont-Farmington Hills. If accrual to the study is unsatisfactory, advertisements will be placed after approval of the IRB.

#### **3.3.2 Eligibility Criteria**

Patients must meet all eligibility criteria to be included in the study:

1. Must be 55 years of age or older
2. Patient must meet NINCDS-ADRDA criteria for Alzheimer's Disease
3. Patient must be able to complete Mini-Mental Examination and ADAS-Cog Score Sheets
4. Patient has a Rosin Modified Hachinski Ischemic Score of less than or equal to 4
5. Patient has a MMSE score of between 10-20
6. Patient has estimated survival of greater than 12 months
7. Patient or legally authorized representative must be able to give consent

Patients will be excluded from the study if they meet any of the following criteria:

1. The patient has a history of cancer except non-melanoma skin cancer
2. Patient is taking anti-epileptic medication.
3. Dermatological skin disease (lice, ringworm, eczema, or psoriasis) of the scalp.
4. Patient taking Alzheimer medication within the last 3 months, i.e. Exelon, Aricept, Namenda, Reminyl or Epixa.

5. Current presence of a clinically significant major psychiatric disorder (e.g. major depressive disorder, bipolar illness, schizophrenia, etc., according to DSM-IV)
6. Patient currently participating in another Clinical Trial.
7. Patient and legally authorized representative unable to give informed consent
8. Patient has history of focal neurological deficits (with the exception of vibratory peripheral neuropathy)
9. Non-Alzheimer dementia
10. Patient has previous history of CNS radiation
11. Patient has evidence of substance abuse (alcohol / or other drugs of dependence) during previous 12 months
12. Patient has history of subdural hygroma / subdural hematoma
13. Patient has history of cerebral infection / hemorrhage
14. Patient has history of being immunocompromised
15. Patient has history of seizure activity
16. Patient has history of hydrocephalus

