### **3.4 Pre-treatment Evaluation and Management**

The following tests/evaluations will be completed prior to initiation of treatment:

- 1) Informed consent: If determined that patient has cognitive impairment which includes decision making capability, a LAR will be used as appropriate for this potentially vulnerable population.
- 2) Consultation with Co-Investigators(Geriatrics/Neuro Specialists) to assess suitability.
- 3) The mini-mental state examination (MMSE)
- 4) The Alzheimer's Disease Assessment Scale2r-Cognitive Subscale(ADAS-Cog)
- 5) Baseline Quality of life questionnaires (QOL-AD; QUALID)
- 6) Pre-treatment Amyvid PET/CT Scan
- 7) Consultation with Radiation Oncologist Investigator prior to enrollment
- 8) History and Physical

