### **3.6 Pretreatment Amyvid PET/CT Scan**

Amyvid (Florbetapir-F18) is a radiopharmaceutical compound approved by the FDA as a diagnostic tool in AD. Amyvid binds to amyloid- $\beta$  with a half-life of 110 minutes. The tracer significantly accumulates more in brains of patients with AD particularly in the regions known to be associated with amyloid- $\beta$  deposits [57]. A negative Amyvid scan indicates sparse to no amyloid- $\beta$  neuritic plaques and is inconsistent with a neuropathological diagnosis of AD at the time of image acquisition. A positive Amyvid scan indicates moderate to frequent amyloid neuritic plaques; neuropathological examination has shown this amount of amyloid neuritic plaque is present in patients with AD, but may also be present in patients with other types of neurologic conditions as well as older people with normal cognition. Amyvid will be administered at a dose of 370 MBq (10 mCi) administered as a single intravenous bolus in a total volume of 10 mL or less. Following the injection, an intravenous flush of 0.9% sterile sodium chloride will be administered. A 10-minute PET image will be acquired starting 30 to 50 minutes after Amyvid intravenous injection. The patient will be supine and the head positioned to center the brain, including the cerebellum, in the PET scanner field of view. Reducing head movement with tape or other flexible head restraints may be employed. Image reconstruction will include attenuation correction with resulting transaxial pixel sizes between 2 and 3 mm. Amyvid images will be interpreted only by the study designated board certified nuclear radiologist. The current guidelines for display and interpretation of Amyvid images will be followed (Appendix VII). Briefly, images will be displayed in the transaxial orientation with access as needed to the sagittal and coronal planes. In reviewing the images, all transaxial slices of the brain will be included using a black-white scale with the maximum intensity of the scale set to the maximum intensity of all the brain pixels. The brain slice with the highest levels of image contrast (highest radioactivity signals for Amyvid uptake) will be located and the contrast adjusted appropriately. Image interpretation will be initiated by displaying slices sequentially from the bottom of the brain to the top. Image interpretation is based upon the distribution of radioactive signal within the brain; clinical information is not a component of the image assessment. Images are designated as positive or negative by comparing the radioactivity in cortical gray matter with activity in the adjacent white matter.

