### **3.12 Stopping Rules**

This study will be stopped for any of the following reasons

- 1) Any patient death attributed to treatment
- 2) Any patient who develops a Grade IV adverse event
- 3) More than 3 of 15 patients who develop a Grade 3 adverse event as per CTCAE v.5.0 in either group
- 4) 50% or more patients in either group have no change or increase in amyloid based on Amyvid PET Scan

- 5) 5 patients that show greater than 4 point deterioration in MMSE in two consecutive cognition evaluations
- 6) 5 patients that show increases greater than 7 on ADAS-Cog scale.

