### **Inclusion Criteria for Eligibility (All responses must be Yes)**

**Yes    No**

- \_\_\_\_\_ 1. Patient is 55 years of age or older
- \_\_\_\_\_ 2. Patient meets NINCDS-ADRDA criteria for Alzheimer's Disease
- \_\_\_\_\_ 3. Patient must be able to complete Mini-Mental Examination and ADAS-Cog Score Sheets
- \_\_\_\_\_ 4. Patient has a Rosin Modified Hachinski Ischemic Score of less than or equal to 4
- \_\_\_\_\_ 5. Patient has a MMSE score of between 10-20
- \_\_\_\_\_ 6. Patients has estimated survival of greater than 12 months
- \_\_\_\_\_ 7. Patient or legally authorized representative is able to give consent

Investigator Signature \_\_\_\_\_

Date \_\_\_\_\_

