**Table 7: Amyvid Correct and Erroneous Scan Results by Reader Training Method among Autopsied Patients**

Read Result		In-Person Training (Study Two)					Electronic Media Training (Study Three)				
		Reader					Reader				
		1	2	3	4	5	6	7	8	9	10
All Scans with Autopsies (N=59 a )	Correct	55	56	53	56	45	49	54	46	53	51
	False Negative	3	2	5	3	12	8	3	12	5	7
	False Positive	1	1	1	0	2	2	2	1	1	1

a 39 positive and 20 negative based on histopathology

Study Three included images from subjects who did not have a truth standard (20 healthy volunteers, 52 patients with mild cognitive impairment, 20 patients with AD) as well as all 59 of the patients who underwent an autopsy (same patients as in Study Two) and provided a truth standard. Duplicate images of 33 patients were included within the total pool of images in order to assess intra-reader image reproducibility. Among the 151 subjects, the median age was 76 years (range 47 to 103), half were females and most were Caucasian (93.4%). Performance characteristics for patients with a truth standard are shown above (Tables 6 and 7). The major reproducibility results are shown in Table 8 for various groups of subjects. Inter-reader reproducibility analyses for all images showed an overall Fleiss' kappa statistic of 0.83 (95% CI: 0.78 to 0.88); the lower bound of the 95% CI exceeded the pre-specified success criterion (95% CI lower bound >0.58). Intra-reader reproducibility analyses showed that, between the two readings for each of the 33 patients with duplicate images, one of the five readers had complete agreement for all 33 patients, two readers had discrepant reads for a single patient, one reader had discrepant reads for two patients and another reader had discrepant reads for three patients.

**Table 8: Number of Positive Amyvid Scan Results within Study Three Subject Groups and Reproducibility of Scan Results Among Readers**

Subject group by cognitive and truth standard (TS, autopsy) status	Positive Scans, n a	Kappa (95% CI)	Percent of Scans with Inter-reader Agreement		
			3 of 5 readers agree	4 of 5 readers agree	5 of 5 readers agree
All subjects with a TS, n=59	33	0.75 (0.67, 0.83)	14	10	76
All subjects without a TS, n=92	33	0.88 (0.82, 0.94)	2	11	87
AD, n=49 (29 with TS; 20 no TS)	38	0.67 (0.58, 0.76)	10	14	76
MCI, n=57 (5 with TS; 52 no TS)	17	0.91 (0.83, 0.99)	2	7	91
Cognitively normal without TS, n=20	4	0.83 (0.69, 0.97)	5	5	90

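### The baseline Amyvid scan has no bearing on eligibility, so a scan-negative patient can be irradiated and can then count only towards stopping rule 4

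*Combined protocol and SAP*

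**What the plan says.** Entry rests on a clinical diagnosis. Inclusion 2 in section 3.3.2 is "Patient must meet NINCDS-ADRDA criteria for" Alzheimer's disease, and the Appendix I checklist repeats it as "Patient meets NINCDS-ADRDA criteria for Alzheimer's Disease". None of the 7 inclusion and 16 exclusion criteria mentions the amyloid scan. Exclusion 9 bars "Non-Alzheimer dementia" but does not say how that is established.

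The Schema, section 3.4 and the Study Calendar all require a pretreatment Amyvid scan. None requires a particular result or says what follows a negative one. Section 3.4 also lists "Consultation with Co-Investigators(Geriatrics/Neuro Specialists) to assess suitability", with no reference to the scan.

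Section 3.6 says that a negative scan indicates sparse to no plaque and "is inconsistent with a neuropathological diagnosis of AD at the time of image acquisition". It has the reader call each scan positive or negative. Section 3.11 analyses the 4-month scan in the same way.

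Stopping rule 4 in section 3.12 is met if "50% or more patients in either group have no change or increase in amyloid based on Amyvid PET Scan". It does not restrict the count to patients who were positive at baseline.

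**The concern.** Section 1.4 presents radiation as an anti-amyloid strategy, and section 1.5 supports it with plaque reduction in mice. The protocol takes a scan that bears on whether a patient has the intended target, says that a negative result does not fit the diagnosis, and then leaves the result unused. Two investigators could handle the same scan-negative patient differently and both be following the protocol.

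Two things are at stake. First, whole-brain irradiation could be given to a patient whose scan speaks against the stated rationale, without the protocol saying that this is intended. Second, on a two-category read a patient who starts negative has nowhere to go but unchanged or increased. Both outcomes count towards rule 4, so that patient is counted towards stopping before treatment begins. The same patient adds no information on amyloid reduction to the correlation in section 2.4, endpoint 3.

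**Working it through.** **The plan's own figure.** Section 3.1 gives one-sided upper limits for 0 events in 15 patients. The formula 1 − (1 − c)^(1/15) gives 26.4%, 18.1% and 14.2% for c = 0.99, 0.95 and 0.90, as stated. These limits do not involve the scan and are not in question.

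**Inputs.**
- Group size: 15 evaluable patients per arm (section 3.9).
- Rule 4 threshold: 50% of 15 is 7.5, so the rule is met at 8.
- Scan-negative share f: the documents give no figure for this population. The nearest is Table 8 of the label in Appendix VII, row "AD, n=49 (29 with TS; 20 no TS"), where the median number read positive across five readers is 38. That gives f = (49 − 38)/49 = 11/49 = 22.4%. I use 5% to 22.4%, with 5% as an assumed lower end.
- Chance q that a scan-positive patient shows no reduction: not in the documents. It is an assumption, varied below.

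**Why 22.4% is treated as an upper figure.** In Table 8, 33 of the 59 autopsied patients were read positive (median), whereas the Table 7 footnote gives 39 positive on histology, a net shortfall of 6. The label does not say how many of those 6 had clinical AD. If all did, the truly negative share would be (11 − 6)/49 = 5/49 = 10%.

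**Chance of at least one scan-negative patient in 15:** 1 − (1 − f)^15.
- f = 5%: 0.75 expected; chance 54%.
- f = 10%: 1.5 expected; chance 79%.
- f = 22.4%: 3.4 expected; chance 98%.

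**Chance that rule 4 is met.** A scan-negative patient always counts, and a scan-positive patient counts with probability q. Each enrolled patient therefore counts with probability p = f + (1 − f)q, and the chance is P(X ≥ 8) for X ~ Binomial(15, p). For example, with f = 22.4% and q = 0.3, p = 0.224 + 0.776 × 0.3 = 0.457.

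| q | f = 0 | f = 5% | f = 10% | f = 22.4% |
|---|---|---|---|---|
| 0.2 | 0.4% | 1.3% | 3.4% | 17% |
| 0.3 | 5% | 9% | 15% | 37% |
| 0.4 | 21% | 29% | 38% | 61% |
| 0.5 | 50% | 58% | 65% | 81% |
| 0.7 | 95% | 96% | 97% | 99% |
| 0.8 | 99.6% | 99.7% | 99.8% | 99.9% |

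**For a fixed number k of scan-negative patients at q = 0.3:** P(Y ≥ 8 − k) for Y ~ Binomial(15 − k, 0.3) is 5%, 9%, 17%, 28% and 43% for k = 0 to 4. With k = 3, only 5 of the other 12 need to show no reduction.

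Scan-negative patients alone would rarely meet the rule: P(at least 8 of 15 negative) is 0.9% at f = 22.4%.

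**The case against.** The strongest objection is about scale. On the positive/negative read, a scan-positive patient shows a reduction only by becoming negative at 4 months, because positive that stays positive is also unchanged. A value of q as low as 0.2 or 0.3 then means that 70% to 80% convert, and nothing in the documents supports that. If q is really 0.7 or more, rule 4 is met almost regardless of who is enrolled, and the main weakness is the undefined meaning of unchanged. If instead a finer scale was intended, as the mention of amyloid number, size and location in sections 2.2 and 2.4 might suggest, a patient with sparse plaque could in principle show a decrease. This objection stands against any single figure for the effect. It does not remove the gap: sections 3.6 and 3.11 describe only the two-category read, and on that read a scan-negative patient can only add to the count.

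A reader might infer that 22% of enrolled patients would lack the pathology. The documents do not support that. The 11 of 49 rests on a median across readers in a mixed sample, partly of autopsied, terminally ill patients, not known to have been selected on this trial's criteria. In the same study median reader sensitivity was 82%, range 69% to 92% (Table 6), so some negative reads are false.

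A reader might also infer that nothing prevents a scan-negative patient from being treated. That goes too far. Exclusion 9 and the suitability consultation give an investigator grounds to decline such a patient. What is missing is an explicit link to the scan.

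Finally, enrolling on clinical criteria alone is a legitimate choice for a descriptive safety study. But the protocol does not say that it intends to treat scan-negative patients or how they count in rule 4.

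**Conclusion.** The point holds as a gap between sections. The scan is mandatory, section 3.6 says what a negative result means, and neither eligibility nor rule 4 takes account of it. At 5% to 22% scan-negative, a cohort of 15 has a 54% to 98% chance of including at least one such patient. The direction of the effect on rule 4 is always towards stopping. Its size depends on q: from 5% to between 9% and 37% at q = 0.3, and little change at q = 0.7 or more, where the rule is met about 95% of the time or more anyway. Both f and q are uncertain, so these are illustrations and not forecasts.

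It would be tempting to conclude that the trial's safety findings are compromised. They are not: the primary endpoint is toxicity, the analysis is descriptive, and the limits for 0 of 15 are unchanged. The consequences fall on patient exposure, on rule 4 and on the secondary amyloid correlation. The change should be made, but the primary analysis does not depend on it.

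**What to change.** Reconcile sections 3.3.2, 3.6 and 3.12 and Appendix I:
- State how the baseline scan result, read before the first fraction, bears on inclusion 2 and exclusion 9, and add the matching item to the checklist. Whether a positive scan is required for entry is for the sponsor and the investigators to decide and justify.
- Evaluate rule 4 and the amyloid correlation only in patients with a positive baseline scan, and state that denominator in 3.12 and in the Schema.

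No extra procedure is needed for treated patients, because the scan is already taken before treatment. If a positive scan is required for entry, 15/(1 − f) patients are scanned per 15 treated: 15/0.95 = 15.8 to 15/0.776 = 19.3, or about 16 to 19. Accrual is slightly slower, and some patients with falsely negative reads are turned away. If it is not required, rule 4 has a smaller denominator: with 3 scan-negative patients, 50% becomes 6 of 12, and each result weighs more.

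This does not settle what unchanged means for a scan that is positive both times. That definition is also needed before rule 4 can be applied.
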